12-months long. Consequently, this study is expected to take a total of 15 to 17 months from beginning of enrollment to completion of follow-up. Additionally, study blinding will be removed after the last subject completes their six-week follow-up timepoint, and 6 and 12-month follow-up will be collected unblinded. Data will be submitted for regulatory

study follow-up after 6 and 12 months.

Participant Duration: Intervention will occur at the time of surgery and subjects will complete a

12-month follow-up program, including in-person visits at one week, six weeks, and six months, as well as a telephone follow-up at 12-months.

review following unblinding at six weeks, and again after completion of

Statistical Methods: Analysis Populations:

Intent-to-treat population (ITT): This population will include all subjects enrolled and randomized to test or reference treatment. Subjects will be analyzed according to the treatment to which they were randomized,

regardless of the treatment they actually received.

Safety population: This population will include all subjects enrolled and randomized to test or reference treatment. Subjects will be analyzed according to the treatment that they received; patients randomized to the reference arm that receive Zip-stitch™ will be included in the Zip-stitch™ safety population. Similarly, patients randomized to the Zip-stitch™ arm that receive sutures will be included in the reference safety population.

Primary and secondary efficacy endpoint analyses will be performed on the ITT population. All safety analyses will be performed on the Safety population.

Efficacy Analysis:

Unless otherwise stated the analyses of efficacy endpoints will be based on the ITT population as follows.

One-sided endpoint analyses will be performed with 80% statistical power; corresponding *p*-values will be reported, and all two-sided analyses and comparisons between groups will be performed assuming a 0.05 significance level. The corresponding *p*-values and 95% confidence intervals (CIs) will be reported.

Primary Efficacy Endpoint:

Frequency of spontaneous implant passing events will be reported through six weeks. Event frequency will be numerically compared to a performance target of 5%.

Secondary Efficacy Endpoints:

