3.2 SECONDARY ENDPOINTS

(1) Binary assessment of cuff closure

Cuff closure will be assessed by an independent surgeon at one and six weeks, as well as at six months. Surgeon visual assessment will grade vaginal cuffs as closed or not closed, or the surgeon may indicate that it was not possible to determine. As such, subjects who experience a dehiscence and are considered a failure in analysis of the primary study safety endpoint will be a failure in this secondary endpoint (lack of closed cuff at six weeks). However, subjects could fail this secondary endpoint without failing the primary study safety endpoint.

In cases in which a surgeon is unable to assess cuff closure, the most recent successful evaluation of cuff closure (including intra-operative evaluation) will be used; reason for inability to determine will be recorded. Fisher's Exact Test will be used to assess possible significance of a difference in cuff closure scores between test and reference groups.

(2) Binary assessment of cuff healing

Vaginal cuff healing will be visually assessed by an independent surgeon at six weeks and six months. Surgeon visual assessment will grade vaginal cuffs as healed or not healed, or the surgeon may indicate that it was not possible to determine. In cases in which a surgeon is unable to assess cuff healing, the most recent successful evaluation of cuff closure will be used. If no prior evaluation has established cuff healing, the cuff will be assumed to have not healed yet. Reason for inability to determine healing will be recorded. Fisher's Exact Test will be used to assess possible significance of a difference in cuff closure scores between test and reference groups. Additionally, healing will be characterized using a predetermined list of binary assessment questions, these will not be statistically compared, but serve to characterize individual healing scores.

(3) Comparison of implant passing rates

The percentage of subjects experiencing implant (either clip or suture) passing by six-weeks and six-months post-operative will be compared between test and control groups using Fisher's Exact Test.

(4) Frequency of implant passing events associated with an Adverse Event

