6.5.1 RESCUE TREATMENT

In the event that a subject is enrolled, and a random treatment is assigned, but the surgeon is unable to achieve cuff closure with the assigned cuff closure method, the surgeon may close the cuff using an alternate method. This event would be considered a protocol deviation and these subjects will be included in analysis of the primary efficacy outcome. These subjects will also be included in secondary endpoint ITT and safety populations, and subject safety data will be included in study analysis.

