9.3 POPULATIONS FOR ANALYSES

Intent-to-treat population (ITT): This population will include all subjects enrolled and randomized to test or reference treatment. Subjects will be analyzed according to the treatment to which they were randomized, regardless of the treatment they actually received.

Safety Population: This population will include all subjects enrolled and randomized to test or reference treatment. Subjects will be analyzed according to the treatment that they received; patients randomized to the reference arm that receive Zip-stitch™ will be included in the Zip-stitch™ safety population. Similarly, patients randomized to the Zip-stitch™ arm that receive sutures will be included in the reference safety population.

Primary and secondary efficacy analyses will be performed on the ITT population. All safety analyses will be performed on the Safety population.

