9.4.4 ANALYSIS OF SECONDARY EFFICACY ENDPOINTS

Secondary Endpoint (1) Cuff closure (compared between test and reference groups) will be assessed (yes or no) by an independent surgeon at one and six weeks, as well as at six months.

Data collection: Surgeon will visually assess vaginal cuff closure, indicating whether the vaginal mucosa is intact. If the vaginal cuff closure is determined not to be intact, then failure of this study endpoint will be indicated and the subject will be included in the ITT population for remaining study endpoints. If additional surgical intervention is necessary to address lack of cuff closure, follow-up will restart following the new procedure date. In this circumstance the new follow-up schedule will be included in the evaluation of remaining efficacy endpoints in the ITT population and will be included in the safety population.

Acceptance Criteria: Endpoint success at each timepoint is defined as test group cuff closure failure rate less than or equal to that of the reference group.

Statistical Analysis Method: A two-sided Fisher's Exact Test will compare (test versus reference) rate of dehiscence at each timepoint. Assessment of this endpoint is independent of primary study endpoint results.

Secondary Endpoint (2) Cuff healing (compared between test and reference groups), will be assessed (yes or no) by an independent surgeon at six weeks and six months.

Data collection: Surgeon visual assessment of cuff healing is limited to a single binary assessment ("healed" or "not healed"). Additional descriptive observations are included during data collection but are not used in comparative analysis. If the vaginal cuff is determined not to be healed, then failure of this study endpoint will be indicated. If additional surgical intervention is necessary, follow-up will restart following the new procedure date. In this circumstance the new follow-up schedule will be included in the evaluation of remaining efficacy endpoints in the ITT population and will be included in the safety population.

Acceptance Criteria: Endpoint success is defined as a test group cuff healing failure rate less than or equal to that of the reference group.

Statistical Analysis Method: A two-sided Fisher's Exact Test will compare (test versus reference) rate of visually assessed, failed cuff healing at each post-operative timepoint. Assessment of this endpoint is independent of the primary safety endpoint.

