9.4.5 ANALYSIS OF SECONDARY SAFETY ENDPOINTS

The Safety population will be the analysis population for all safety analyses.

Secondary Endpoint (5) Comparison of incidence of adverse events.

Data collection: Adverse Events will be tabulated for both the test and reference groups. All AEs and SAEs will be MedDRA-coded and summarized by treatment arm. In addition, the number and proportion of AEs and SAEs will be calculated for each group. For each MedDRA-coded medical term, the proportion of subjects who experience at least one of the following will be reported and compared.

Adverse event

- Adverse event related to treatment
- Serious adverse event
- Serious adverse event related to treatment
- Adverse event leading to study discontinuation
- Serious adverse event leading to study discontinuation

Classification of AEs will also be presented and compared. Events will be reported by MedDRA system organ class and preferred term. Adverse Events will be compared by severity and device relatedness between the test and reference groups.

Acceptance Criteria: There is no defined endpoint acceptance criteria for the comparison of adverse events.

Statistical Analysis Method: A two-sided Fisher's Exact Test will compare (test versus reference) rate of incidence of adverse events by six months post-operative. Assessment of this is independent of the primary study endpoints.

Secondary Endpoint (6) Comparison (test to reference group) of non-increase in subject dyspareunia scores from baseline to 6-months post-operative.

Data collection: Individual subject dyspareunia will be assessed using the relevant sexual discomfort module of the validated Female Sexual Function Index (FSFI). Higher scores indicate good sexual function with little or no sexual discomfort, and lower scores indicate poor sexual function with higher levels of sexual discomfort. Scores of zero indicate no sexual activity and will not be included in comparison of non-increase in dyspareunia.

Acceptance Criteria: A subject level failure is defined as a decrease in sexual function score (signifying an increase in dyspareunia). Endpoint success is defined as the same or lower rate of FSFI score decrease in the test group at six months when compared to the reference group at six months.

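### The as-treated Safety grouping moves Zip-stitch subjects sutured after a failed clip closure to VICRYL, and endpoints 5 to 7 have no by-randomised-arm counterpart

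*Combined protocol and SAP*

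**What the plan says.** Section 9.3 defines the Safety population by treatment received. Patients randomised to the Zip-stitch "arm that receive sutures will be included in the reference safety population". The synopsis (1.1) repeats the rule: those in the Zip-stitch arm "that receive sutures will be included in the reference safety population". Section 9.3 adds: "All safety analyses will be performed on the Safety population".

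Section 6.5.1 shows how such subjects arise. If closure cannot be achieved with the assigned method, "the surgeon may close the cuff using an alternate method". On populations it says: "These subjects will also be included in secondary endpoint ITT and safety populations". It does not say which safety group they join, so the 9.3 rule decides.

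For adverse events (endpoint 5), section 9.4.5 plans a Fisher test of the "rate of incidence of adverse events by six months post-operative", on the Safety population. Dyspareunia (6) and pain (7) are in the same section and use the same population. Each counts as a success when the test-group failure rate does not exceed the reference rate.

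Dehiscence is also captured elsewhere. Under section 3.2, a subject "considered a failure in analysis of the primary study safety endpoint will be a failure in this secondary endpoint" (cuff closure). Section 9.4.4 analyses that endpoint on ITT with a Fisher test that "will compare (test versus reference) rate of dehiscence at each timepoint".

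**The concern.** As-treated grouping is meant to attribute events to the device a subject was exposed to. Here a subject can be labelled VICRYL precisely because the clips failed, even if clips remain in the cuff. Section 2.3.2 names a clip-specific hazard, a misplaced clip impinging on the bladder with later erosion. If that clip stayed in a cuff finished with suture, the literal rule would count the erosion against suture.

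With about 20 reference subjects, one or two moved subjects are visible in the rates. Section 3 says that data through six months may support market clearance, and section 4.2 accepts that the small reference arm weakens safety comparisons.

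**Working it through.** **Inputs.** Enrolment goal 39 test and 20 reference (9.2); grouping rule (1.1, 9.3); rescue (6.5.1); endpoint criteria (9.4.4, 9.4.5). Rescue and event rates are not given, so every count below is an assumption.

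**1. The plan's own figure.** 35/(1 − 0.10) = 38.9, so 39; 39/2 = 19.5, so 20; total 59. It reproduces.

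**2. Where a Zip-stitch subject rescued with suture is counted.**

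| Outcome | Population | Counted under | Version by randomised arm |
|---|---|---|---|
| Primary safety, dehiscence | Safety | VICRYL | Yes: endpoint 1 on ITT |
| Endpoint 5, adverse events | Safety | VICRYL | None, except events tied to implant passing (endpoint 4, ITT) |
| Endpoint 6, dyspareunia | Safety | VICRYL | None |
| Endpoint 7, pain | Safety | VICRYL | None |

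**3. Expected shift.** Let k of 39 be rescued, with risk p in everyone else in both arms and p + d in the rescued.
- Test minus reference as randomised: kd/39.
- As written: −kd/(20 + k).
- Shift: −kd[1/39 + 1/(20 + k)].

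For k = 1, 2, 4 the shift is −0.073d, −0.142d, −0.269d. Each 10 points of excess risk in rescued subjects thus moves the difference 0.7, 1.4 or 2.7 points towards Zip-stitch. With d = 0 the mean shift is zero. If the arms truly differ and rescued subjects carry the test-arm risk, the difference shrinks by the factor 20/(20 + k): 0.91 for k = 2 and 0.83 for k = 4.

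**4. Noise when d = 0.** Simulation with a 30% event risk in everyone: the observed direction flips in favour of Zip-stitch in about 6% of trials (5% rescued) or 9% (10% rescued), and against it in about 5% or 7%.

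**5. Numerical criteria, endpoints 6 and 7 (assumed counts).**
- One rescued subject who fails: 8/39 (20.5%) vs 4/20 (20.0%) fails as randomised; 7/38 (18.4%) vs 5/21 (23.8%) succeeds as written.
- Four rescued subjects who do not fail: 7/39 (17.9%) vs 4/20 (20.0%) succeeds as randomised; 7/35 (20.0%) vs 4/24 (16.7%) fails as written.

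These use full enrolment. Six-month denominators will be smaller, and smaller again for dyspareunia, where zero scores are left out.

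**6. Adverse events (assumed counts).** Two rescued subjects, both with an event: 13/39 (33.3%) vs 6/20 (30.0%) becomes 11/37 (29.7%) vs 8/22 (36.4%). Two-sided Fisher p = 1.00 and 0.77. At a 30% risk, both having an event has probability 0.3² = 9%.

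**7. Dehiscence.** If the only case is in a single rescued subject, the primary safety table changes from 1/39 (2.6%) vs 0/20 to 0/38 vs 1/21 (4.8%); p = 1.00 and 0.36. Endpoint 1 on ITT still shows 1/39 vs 0/20.

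**8. Stopping rule (10.1.2).** The review after a pause counts failures with the test device but does not say how rescued subjects are attributed. At 59 enrolled, 3 cases are 5.08% and 2 are 3.4%, so the attribution of one case can decide whether the criterion is met. The pause trigger pools both arms and is unaffected.

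**The case against.** The strongest reply is that little is hidden. Dehiscence is compared by randomised arm in endpoint 1. Adverse events are also summarised by device relatedness (3.2, 9.4.5), graded separately for each event (8.3.3). Endpoint 4 reports passing-related events on ITT. Rescues are logged as deviations, safety data are listed by subject, and an independent physician adjudicates safety events (10.1.5). The as-treated rule is symmetric, the secondary endpoints are unpowered, and endpoint 5 has no acceptance criterion. Surgeons are trained in clip removal and replacement (6.1.2), and inadequate cuff tissue is an exclusion before randomisation (5.2), so rescues may be few.

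Most of this stands, and it sets the size of the point. These safeguards make a case traceable; they do not correct the endpoint 5 to 7 comparisons, and endpoints 6 and 7 do have pass/fail criteria.

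Three stronger readings are tempting, and the documents do not support them:
- *That dehiscences after failed clip closure disappear from the Zip-stitch results.* Endpoint 1 keeps them there.
- *That the rule systematically favours Zip-stitch.* That needs a higher event risk in rescued subjects, for which the documents give no figure. Rescued subjects without events push the other way.
- *That section 9.4.10 would overwrite an observed dehiscence.* It sets a rescued case's primary endpoint value to missing and imputes it, but its context is implant passing, and 6.5.1 says that safety data of rescued subjects are analysed. The wording is loose because dehiscence is also a primary endpoint; a clarification is enough.

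**Conclusion.** The concern holds in limited form. The stated rule, not a missing detail, moves rescued Zip-stitch subjects to VICRYL for endpoints 5 to 7 and for the primary dehiscence table, and for endpoints 5 to 7 no general comparison by randomised arm is planned. The mixed clip-and-suture cuff is undefined; its VICRYL label follows only from the literal wording.

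The size depends on two unknowns, the rescue rate and the excess risk in rescued subjects. The only related experience is ten successful closures out of ten (2.2). The exact 95% upper limit for failure from 0/10 is 1 − 0.025^(1/10) = 30.8%, which excludes neither no rescues nor about 12 of 39; the upper end is a bound, not an expectation. With equal risk throughout, the rule adds noise and no mean shift. With higher risk in rescued subjects, it favours Zip-stitch. None of the dehiscence or adverse event illustrations above is statistically significant under either grouping. The practical exposure is in the purely numerical criteria of endpoints 6 and 7 and in the reading of the adverse event tables. Severity is low to moderate.

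Section 9.4.3 defines the primary safety endpoint through six months, against six weeks in 1.1 and 3.1, and omits the Fisher comparison stated in 3.1. That is a separate finding and adds no weight here.

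**What to change.** - In 9.3 and the synopsis, keep in the Zip-stitch safety group any subject in whom a clip was applied or attempted. This also settles the mixed closure.
- Report endpoints 5 to 7 and primary dehiscence by randomised arm alongside, and list rescued subjects by arm.
- State in 9.4.10 that the set-to-missing and imputation rule covers implant passing only.
- Reconcile 10.1.2 with 9.3 on how rescued subjects are counted. No change to the stopping rule is proposed.

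The cost is wording in four places, a small set of tables and one listing, with no change in sample size. The intra-operative form must record attempted and retained clips; the protocol does not say whether it does. The downside is that mixed closures, including reference subjects rescued with clips, fall under Zip-stitch even when suture caused the event. The tables by randomised arm offset this. The choice should be fixed before the six-week unblinding, so that it cannot be read as post hoc.

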9.4 STATISTICAL ANALYSES

9.4.1 GENERAL APPROACH

In general, continuous variables will be summarized by providing the number of subjects with available data (n), the mean, median, standard deviation, minimum, and maximum values. For categorical variables, the number and percentage of subjects that are in each category will be provided. Unless otherwise specified (such as for the primary endpoint), the denominator for percentages will be all relevant subjects in a particular analysis, excluding those for whom data are not available prior to the relevant endpoint timepoint. For subjects lost to follow-up prior to evaluation of an endpoint, their data will be subject to the data imputation plan detailed in Section 9.4.10.

The ITT population will be the analysis population for all efficacy analyses.

Statistical analyses will be performed using SAS v9.4 or later (SAS Institute Inc., Cary, NC, USA).

9.4.2 ANALYSIS OF THE PRIMARY EFFICACY ENDPOINT

The primary efficacy endpoint in this study is frequency of implant passing incidents evaluated through six weeks post-operative. Subjects who report an implant passing event up to six weeks after surgery

will be asked to collect and return the passed implant, and to come in for a follow-up visit within two weeks. If there is no planned visit within that window, the subject should have an unscheduled visit as soon as they are able. The surgeon will first confirm that it was an implant that was passed, then during the visit, a visual surgeon assessment of cuff closure, healing, and assess any possible relationship of implant passing to adverse events (secondary efficacy endpoint 4).

The final analysis of the primary efficacy endpoint will be implant passing rate, which will be numerically compared to the established 5% performance target.

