Frequency of implant passing incidents found to be associated with an Adverse Event will be reported. Failure in this endpoint is defined, on a per patient basis, as the presence of a spontaneous implant passing event (one or more clips being passed) determined by a blinded study investigator to be associated with an Adverse Event (AE), where "Associated" is defined as a device-related AE that is temporally related to the implant passing event. See Section 9.4.2 for a detailed description of investigator determination of Adverse Event relatedness to implant passing events.

Frequency of implant passing (either clips or sutures) will be explicitly collected at each followup visit; however, events may be reported between visits or during unexpected visits. When implant passing is reported, subjects will be asked to collect and provide passed implants, and an in-person evaluation will be performed, involving a visual cuff closure and healing assessment.

(5) Comparison of Incidence of adverse events

The number of adverse events and serious adverse events, as well as the proportion of subjects with adverse events, will be summarized by treatment arm, severity, and relatedness to device. Adverse events will be coded using the validated MedDRA system. By-subject listings will be provided for all safety data. Incidence of adverse events will then be compared using Fisher's

Exact test to assess possible significance or relationship of cuff closure device to adverse event rate.

(6) Comparison of change in dyspareunia

Dyspareunia will be pre-operatively baselined and assessed at each follow-up timepoint, including any unexpected visits, using the sexual pain and discomfort domain (four questions) from the validated Female Sexual Function Index (FSFI).^{21,22} Individual success is defined as non-increase in dyspareunia from baseline to six months. Fisher's Exact Test will be used to compare this measure between test and reference groups.

(7) Comparison of change in pain

Patient pain will be pre-operatively baselined and assessed at each follow-up timepoint, including any unexpected visits, using a validated 11-point numerical rating scale²³ (no pain: 0 – the most pain: 10). Individual success is defined as non-increase in pain between baseline and six months. Fisher's Exact Test will be used to compare this measure between test and reference groups.

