Follow-up will take place in person at one week, six-weeks, and six-months, as well as by telephone at 12-months. Follow-up will be performed by an independent co-investigator who is blinded to the treatment received (investigator who did not complete the procedure and does not have access to the blinded treatment assigned). Data capture will be performed using a validated electronic data capture system (MedNet Solutions, Minnetonka, MN).

Evaluation of the primary study endpoints will be complete after the six-week in-person follow-up visit. Secondary endpoint results will also be collected through the six-month visit and additional data will be collected through 12-months. The primary analysis of the data from this study will be performed when the six-week data are available. Data collected after 6 weeks will be reported in supplemental follow-up reports.

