4.2 SCIENTIFIC RATIONALE FOR STUDY DESIGN

The primary objective of this study is to evaluate the efficacy and safety of the Zip-stitch™ Vaginal Cuff Closure system. This will be accomplished by measure of the frequency of implant passing events and the frequency of postoperative vaginal cuff dehiscence, respectively.

This study has been sized and designed in response to FDA recommendations regarding primary safety and efficacy concerns. Determination of rate of implant passing and determination of failed vaginal cuff closure are evaluable within the sample size previously proposed by the Agency.

As the primary efficacy endpoints are not comparative to the reference arm, the 2:1 reference group sizing is appropriate for the reference arm of this study. There are limitations to this reference group sizing strategy; primarily, smaller sample sizes provide weaker comparative information for safety and secondary endpoints.

Evaluation of the primary study efficacy endpoint is subject to reporting bias. It is possible that a patient may not realize she has passed an implant, or she may incorrectly report that she has passed an implant. She could, alternatively, pass or report passing multiple degraded part(s) of a single implant. To encourage accurate primary endpoint data collection, patients will be asked to collect and provide to their surgeon(s) any solid objects passed during the post-operative period. If patients do not have a visit schedules within two weeks of reporting an implant passing event, they will come in for an unscheduled

visit as soon as is practical. Events will be recorded as implant passing events only if study personnel can confirm that an implant (or part of an implant) was passed.

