6.3 MEASURES TO MINIMIZE BIAS: RANDOMIZATION AND BLINDING

Variable block size randomization will be employed to assign a vaginal cuff closure method to each subject. At the time of enrollment and after confirmation of intraoperative eligibility, a subject will be randomly assigned treatment (cuff closure) with the test device (Zip-stitch™) or reference device (VICRYL™). This assignment will be provided via sponsor provided randomization envelopes broken down in 2:1 variable block sizes and stratified by site. Treatment allocation blocks will vary from three to six subjects and will be split 2:1 test to reference assignment. This method helps safeguard against a simple randomization generating a smaller than intended test or reference group.

Subjects will be blinded to the cuff closure method they receive during surgery. Because operating surgeons cannot be blinded to the treatment they are providing, this trial cannot be completely double-blinded. Every effort will be made to minimize bias in post-operative data collection. Data collection will be performed by an investigator without access to the blinded to treatment assignment. Treatment assignment will be recorded at the time of procedure in the electronic data capture system. After this point, the investigator collecting follow-up data will be blinded to medical records and treatment group. The operative surgeon cannot be blinded as the performed treatment. They will be available during follow-up as needed but will not participate in data collection for patients that they provided treatment.

Database lock and data un-blinding will take place after completion of the last six-week follow-up visit. Subjects will still participate in the 6 and 12-month visit and extension period call, but data will be unblinded. The data collected at the 12-month telephone visit are limited to pain, dyspareunia, and adverse events. Adverse events are likely to have significant clinical sequelae, and therefore not likely to be forgotten. Pain and dyspareunia are evaluated based on experience in the time frame of the call, and therefore are not affected by recall bias.

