8.3 ADVERSE EVENTS AND SERIOUS ADVERSE EVENTS

8.3.1 DEFINITION OF ADVERSE EVENTS (AE)

Adverse event means any untoward medical occurrence associated with the use of an intervention in humans, whether or not considered intervention-related (21 CFR 312.32 (a)).

Adverse Event details will be classified and reported by a study investigator and confirmed by the study PI. Classifications of adverse events are described below. Clip passing, by itself, is *not* an adverse event.

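### At implant-passing visits the surgeon confirms the returned object before grading closure, healing and AE relation, which undercuts the promised blinding; separately, the clip/suture wording treats the arms inconsistently

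*Combined protocol and SAP*

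**What the plan says.** Section 9.4.2 (primary efficacy analysis) covers women who report a passing event up to six weeks after surgery. They "will be asked to collect and return the passed implant, and to come in for a follow-up visit within two weeks". At that visit "The surgeon will first confirm that it was an implant that was passed, then during the visit, a visual surgeon assessment of cuff closure, healing", followed by an assessment of any relation between the passing and AEs. A planned visit within the window serves as the passing visit; otherwise an unscheduled one is arranged.

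Three sections say the judgements are blinded:

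- 3.2(4) defines an endpoint 4 failure as a passing event "determined by a blinded study investigator to be associated with an Adverse Event (AE").
- 4.1: "Follow-up will be performed by an independent co-investigator who is blinded to the treatment received".
- 6.3: "the investigator collecting follow-up data will be blinded to medical records and treatment group". Of operating surgeons it says: "They will be available during follow-up as needed but will not participate in data collection for patients that they provided treatment".

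Section 4.2 is looser about who confirms the object: "Events will be recorded as implant passing events only if study personnel can confirm that an implant (or part of an implant) was passed".

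On AE counting, 8.3.1 states: "Clip passing, by itself, is *not* an adverse event". It does not mention sutures, although 3.1 defines a passing event for clips or sutures. In 3.2(4), by contrast, the parenthesis describing the endpoint 4 failure mentions clips only.

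**The concern.** Closure, healing and AE causality are matters of judgement, and all are compared between arms. If the assessor handles the returned object first, the grades in women who pass an implant may be given with the arm known. Section 2.3.2 already records that clip passing has not been linked to compromised closure or healing, so there is a prior expectation for knowledge of the arm to act on. Blinding lost in this way cannot be restored at analysis.

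The clip/suture wording is a separate matter. It does not touch closure or healing grades. It bears on how AEs (endpoint 5) and AE-associated passing (endpoint 4) are counted in each arm.

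**Working it through.** **Enrolment figures.** 4.1 gives 35 evaluable test women and 10% loss. 35/0.9 = 38.9, rounded up to 39; 39/2 = 19.5, rounded up to 20; 39 + 20 = 59. This reproduces the plan. For the reference arm I assume the same loss: 20 × 0.9 = 18 evaluable.

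**Does the order conflict with the blinding?** 9.4.2 gives confirmation and grading to the same surgeon, in that order. 4.1 and 6.3 require whoever collects follow-up data to be blinded, and 3.2(4) requires it for the AE link. 9.4.2 asks only whether the object is an implant, not which kind, so disclosure of the arm is an inference. It is a strong one for an intact object: 6.1.2 describes an injection-moulded clip and a running suture, and clips take months to be absorbed. It is weaker for the fragments that 4.2 allows for.

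**How many women?** 4.2 expects a passing rate below 10%, and the performance target is 5%. I use 5% and 10% as an assumed range, the same in both arms. Expected number = n × p; P(at least one) = 1 − (1 − p)^n.

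| Arm | n | Expected, 5% | P(≥1), 5% | Expected, 10% | P(≥1), 10% |
|---|---|---|---|---|---|
| Test | 35 | 1.75 | 0.83 | 3.5 | 0.97 |
| Reference | 18 | 0.9 | 0.60 | 1.8 | 0.85 |

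A passing visit is therefore likely to occur, but in few women.

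**Which endpoints does it reach?** Endpoint 4 directly, because the AE link is judged at that visit. Endpoints 1 and 2 are analysed at scheduled timepoints (9.4.4), so they are reached only if:

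- the passing visit is itself a scheduled visit;
- a later cuff cannot be assessed and the most recent evaluation is carried forward (3.2(1) and (2)); or
- the same assessor sees the woman again.

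**How far can the wording move the comparisons?** These are extremes under stated assumptions, not forecasts.

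- *Endpoint 4* succeeds if the test percentage does not exceed the reference percentage (9.4.4). Let q be the probability, equal in both arms, of a passing event that would count as a failure under one common rule. With 35 and 18 women and a common rule, P(success) is 0.45 at q = 5% and 0.43 at q = 10%. If only clips can count, as 3.2(4) reads, success requires no test events: 0.95^35 = 0.17 and 0.90^35 = 0.03. If only suture passing could count, because it was logged as an AE and clip passing never was, P(success) = 1.00. Not every passing event is AE-associated, so q may well be below the passing rate.
- *Endpoint 5* compares AE incidence. Suppose sites logged suture passing alone as an AE, with any-AE rate b in both arms otherwise. The reference rate then rises by (1 − b) × p. With assumed b of 30% to 50% and p of 5% to 10%, the smallest rise is 0.5 × 5 = 2.5 points and the largest 0.7 × 10 = 7 points.
- *Sensitivity of Fisher's test* to a few events: 0/35 against 2/18 gives two-sided p = 0.11; 0/35 against 3/18 gives p = 0.035.

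**The case against.** A reader might infer that the rules favour the test arm. The documents do not support that. They never call suture passing an AE; they are silent, so any AE advantage to Zip-stitch depends on how sites would log it. The parenthesis in 3.2(4) works against Zip-stitch, since a reference woman could not fail. The definition of an associated AE in 10.2 covers both devices. The endpoint table in Section 3 also uses clip passing loosely where the endpoint concerns implants, so 8.3.1 may be the same habit. What stands is inconsistent wording.

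A reader might also infer that the assessor is unblinded in every woman, or in every woman with an event. That goes too far: only women with a passing event are affected by this route, 4.2 lets study personnel in general confirm the object, and fragments may not be recognisable. 10.2 adds that traditional suture and clips share a polymer, though a shared material does not give them the same shape. None of this removes the stated order in 9.4.2.

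It is fair to add that secondary endpoints are unpowered (4.2, 9.2), that endpoint 5 has no acceptance criterion, and that 6.3 plans unblinding after the last six-week visit (8.1 instead says after the six-month visits). The independent medical monitor adjudicates safety events (10.1.5), but is not stated to be blinded and is given no role in grading closure or healing. Finally, 3.3 has the surgeon record visible implant material at every visit, a wider route to unblinding that reordering one visit does not close. These limits keep the point modest; they do not answer it.

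**Conclusion.** The point holds in limited form. The order in 9.4.2, followed as written, is likely to disclose the arm to the person whom 3.2(4), 4.1 and 6.3 require to be blinded. This is a stated sequence that invites bias, not merely an unspecified detail. It affects women with a passing event through six weeks: about 2 to 4 of 35 evaluable test women if the rate is 5% to 10%, plus any suture passers. It reaches endpoint 4 directly and endpoints 1 and 2 under the conditions listed above. The conclusion rests on the inference that a clip or suture can usually be recognised.

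Separately, 8.3.1 and 3.2(4) treat the arms differently, in opposite directions, in the comparisons of AEs and of AE-associated passing. The net direction cannot be read from the documents, so no claim of a test-arm advantage is justified.

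**What to change.** 1. **Reverse the order in 9.4.2.** The woman returns the object in an opaque container. The blinded assessor enters closure, healing and AE-relation grades before it is opened; the AE-relation grade applies only if an implant is then confirmed. Confirmation is done by the assessor after data entry or by other study personnel, as 4.2 already permits; the latter is preferable when the same assessor will see the woman again. It should not fall to the operating surgeon. Confirmation decides the primary efficacy endpoint, and with 35 test women one event is 1/35 = 2.9% and two are 2/35 = 5.7%, on either side of the 5% target. That call should not go to the unblinded operator whom 6.3 keeps out of data collection.
2. **Record recognition on the CRF.** After grading, the assessor notes whether the implant type was recognised, including from material visible at examination (3.3). Report those grades separately.
3. **Use one wording for both arms.** Write *implant (clip or suture)* in both 8.3.1 and 3.2(4). Correcting only one would leave the other asymmetry in place.

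The cost is protocol and CRF wording, one extra field and a container. Blinding will still fail where an implant is visible at examination; item 2 documents this but does not prevent it.
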